## 12.2 Determination of Sample Size and Power Consideration

The patients will be randomized into 1 of 2 study groups: IQOS or cigarettes. Patients will be analyzed by their actual exposure throughout the course of the study. Therefore, there will be patients who predominantly use IQOS or patients who predominantly use cigarettes, however, there will also be patients who predominantly use other tobacco and nicotine containing tobacco products, or have a pattern of mixed tobacco product use. All patients will continue in the study but will be analyzed based on their exposure pattern during the study. Depending on the patterns of product use observed in the study, sensitivity analyses and descriptive summaries will be implemented.

The statistical hypothesis that will be tested for PD at 6 months is:

- $H_0: X_{IQOS} - X_{cigarette} \leq 0.$
- $H_A: X_{IQOS} - X_{cigarette} > 0.$

Where  $X_{IQOS}$  and  $X_{cigarette}$  are the adjusted mean changes from baseline values (baseline minus endline) of PD for IQOS and cigarettes, respectively. The  $H_0$  is rejected with a one-sided alpha level of 2.5%.

In the literature reviewed, the papers of Rosa [44] and Preshaw [43] are similar to the study described in this protocol, in that they include:

- Some requirements on minimum PD for inclusion
- Comparison of smokers with former smokers
- Means and SDs (or standard errors of the mean and sample size)

Therefore it is assumed that the cigarette arm will have similar results to what is described in the literature for current smokers and that the results in the IQOS arm will be similar to what is observed in former smokers.

Based on the published data and recommendations from the American clinical practice guidelines [85], the following estimates with PD differences and standard deviations between smokers and non-smokers (Table 7) are based on data assessed at 3, 9 and 12 months:

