**Table 7 Sample sizes for PD differences between smokers and non-smokers and standard deviations based on the literature**

SD \ difference (mm)	0.2	0.25	0.3	0.35
	0.4	64	42	29
0.45	81	52	37	27
0.5	100	64	45	33

Abbreviation: SD = Standard deviation

Thus, the sample size selected above gives sufficient power for testing PD.

With alpha of 2.5%, power of 80%, SD of 0.5, and effect difference of 0.25 mm, then sample size needed in each arm is 64 patients. By considering 25% of drop out and product switching, 86 patients per arm, i.e., 172 patients in total, are needed.

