## 12.6 Primary Analysis

The primary analysis evaluates the change from baseline in PD, which will be calculated for each patient across all sites with a baseline PD  $\geq 4$  mm, resulting in one value per patient per endpoint for each visit (baseline, Month 3 and 6).

The primary analysis will be performed on the As Exposed Set using a mixed model for repeated measurements (MMRM) for only subjects who have used cigarettes and/or Heatsticks. The model will include the PD change from baseline as the dependent variable, adjusting for daily cigarette consumption and disease severity at V1, full mouth PD at V1, exposure group and its interaction with visit. Site will be included as a random effect. The modeling assumptions will be evaluated and the model fit will be assessed by the analysis of the residual (diagnostics) and by comparing the values predicted vs. the observed values (calibration).

Additionally, the analysis will be performed on the FAS, PP and Adherent Use populations as a supportive sensitivity analysis. Additional sub group analyses such as for “Other” product use groups may be analyzed and will be defined in the SAP.

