9.1.8 Multiple Comparison/Multiplicity

There will be an adjustment for multiplicity for the secondary testing of CAL and PD within the As Exposed Set, as well as for BoExp. PD at 3 months and CAL at 6 and 3 months will be tested in a hierarchical manner, depending on the outcome of the test at previously specified endpoint in hierarchical testing order. The order of testing is as follows,

The primary analysis, of PD at 6 months will be tested using a one-sided alpha level of 2.5%.

1. PD at 6 months will be tested.

The secondary analysis of PD at 3 months and CAL at 6 and 3 months will be tested in a hierarchical manner, using a one-sided alpha level of 2.5%, depending on the outcome of the test at previously specified endpoint in hierarchical testing order.

1. PD at 3 months will be tested only if the test for PD at 6 months is significant.

2. CAL at 6 months will be tested only if the test for PD at 3 months is significant

3. CAL at 3 months will be tested only if the test for CAL at 6 months is significant.

Additional secondary analysis of the BoExp will be tested, in a hierarchical manner within each BoExp (independent of the other statistical tests being performed), using a one-sided alpha level of 2.5%. The hierarchical order will be:

1. BoExp at 6 months will be tested.

2. BoExp at 3 months will be tested only if the test for BoExp at 6 months is significant.

Total NNAL and CEMA levels (concentration data adjusted for creatinine), analyzed on a logarithmic scale, will be tested at 6 and then 3 months, in that order, so that the testing of each BoExp will stop if the test is not significant.

Confidentiality Statement

Data and information contained in this document are considered to constitute trade secrets and confidential commercial information, and the legal protections provided to such trade secrets and confidential information are hereby claimed under the provisions of applicable law. No part of this document may be publicly disclosed without the written consent of Philip Morris Products S.A

Unless stated otherwise, all statistical tests will be one-sided and conducted at the 2.5% level, and all CIs will be two-sided 95%.

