9.5.1.1 Primary Analyses

Primary Analysis of Change from Baseline in PD at V4	
Population	
 • As Exposed Set For this analysis, subjects categorized in IQOS user, cigarette user or dual user will be included with initial PD \geq 4mm will be included.
	The primary analysis will be performed on the As Exposed Set using a mixed model for repeated measurements (MMRM). Estimates of difference in PD will be calculated for Cigarette User against IQOS User categories and Cigarette User against Dual User categories. The model will include the PD change from baseline as the dependent variable, adjusting for the following covariates; 
 1. Daily cigarette consumption at V1 2. Disease severity at V1 3. Full mouth PD at V1 4. Visit 5. Product use pattern (IQOS user, cigarette smoker or dual user) 6. Interaction between visit and product use

Confidentiality Statement

Data and information contained in this document are considered to constitute trade secrets and confidential commercial information, and the legal protections provided to such trade secrets and confidential information are hereby claimed under the provisions of applicable law. No part of this document may be publicly disclosed without the written consent of Philip Morris Products S.A

Primary Analysis of Change from Baseline in PD at V4

7. Average daily cigarette use at each visit
8. Interaction between Daily cigarette consumption at V1 and product use
9. Interaction between Disease severity at V1 and product use
10. Time since last SRP
11. Number of target tooth/teeth extracted
12. Number of non-measured target tooth/teeth extracted
13. Baseline tooth mobility

Site will be included as a random effect. The degrees of freedom will be adjusted by using Kenward Roger (KR) method. A Toeplitz structure (“type=toep”) will be specified as the covariance matrix. However, other covariance structures may be used in case of non-convergence. Covariates 8-12 will be assessed for adequacy in the model using a step-wise (backward) approach through the following algorithm.

1. Fit a full model using maximum likelihood with all covariates
2. Perform a likelihood ratio test for the full model and drop the covariate with the largest p-value for the likelihood ratio statistic if it is more than 0.05.
3. Drop one covariate (only covariates 7-14) and re-fit the model.

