9.5.3 Exploratory Analyses

Summary Table of Exploratory Analysis to Evaluate the Change in (i) Multiplex assay (MAP) (ii) Parallel Reaction Monitoring (PRM)

Population	:	
 As Exposed Set
Contents	:	
The analysis will be performed on the As Exposed Set using a mixed model for repeated measurements (MMRM).
 
The model will include the log change from baseline as the dependent variable, adjusting for the following covariates;
 
 Daily cigarette consumption Disease severity at V1 MAP/ PRM at V2 Visit Product use Interaction between visit and product use Interaction between Daily cigarette consumption at V1 and product use Average daily cigarette use at each visit Interaction between Disease severity at V1 and product use Time since last SRP Number of target tooth/teeth extracted Number of non-measured target tooth/teeth extracted Baseline tooth mobility Site will be included as a random effect. The degrees of freedom will be adjusted by using Kenward Roger (KR) method. A Toeplitz structure (“type=toep”) will be specified as the covariance matrix. However, other covariance structures may be used in case of non-convergence. Covariates 7-12 will be assessed for adequacy in the model using a step-wise (backward) approach through the following algorithm. 
 Fit a full model using maximum likelihood with all covariates Perform a likelihood ratio test for the full model and drop the

Confidentiality Statement

Data and information contained in this document are considered to constitute trade secrets and confidential commercial information, and the legal protections provided to such trade secrets and confidential information are hereby claimed under the provisions of applicable law. No part of this document may be publicly disclosed without the written consent of Philip Morris Products S.A

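### The primary model's Toeplitz covariance imposes one common variance on months 3 and 6; an unstructured matrix within patient removes that assumption for one extra parameter

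*SAP*

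**What the plan says.** SAP 9.5.1.1 fits a repeated-measures mixed model to PD change from baseline, with a random site effect and Kenward-Roger degrees of freedom. A Toeplitz structure, given as `type=toep`, "will be specified as the covariance matrix. However, other covariance structures may be used in case of non-convergence". Non-convergence is the only stated reason to leave it.

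Protocol 12.6 describes the response as "resulting in one value per patient per endpoint for each visit (baseline, Month 3 and 6". Once the baseline is subtracted, each patient supplies at most two records, V3 and V4, and SAP 9.5.2.1 confirms that both enter the model.

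The sample code in SAP 9.5.1.1 has `REPEATED / subject=visit (subject) type=toep`. It names no repeated effect and makes each visit within a patient its own block.

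The same set-up is used elsewhere. CAL uses the section 9.5.1 model (SAP 9.5.2.1), BoExp points to the same sample code (SAP 9.5.2.1), and the FAS and Per Protocol analyses refer back to the primary analysis (SAP 9.5.1.2 and 9.5.2.2).

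**The concern.** `type=toep` gives every visit the same variance; the heterogeneous form would be `type=toeph`. With two visits the matrix is [[v, c], [c, v]], which is compound symmetry. The V4 contrast then draws its standard error from a variance averaged over V3 and V4.

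Nothing in the documents assures equal variances. Scaling and root planing (SRP) may run to 8 weeks (56 days) after V2, a month is 30 days, and the visit windows are ±7 days at V3 and ±14 days at V4 (Protocol 4, 4.3 and 7.6.2). V3 can therefore fall 90 − 7 − 56 = 27 days after the last planned SRP, and V4 no sooner than 180 − 14 − 56 = 110 days after it, so the visits can catch different stages of healing. The planning estimates "are based on data assessed at 3, 9 and 12 months", with no SD for month 6 and none separated by visit.

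What is at stake is the validity of the primary p-value. Significance of that test is the only success criterion (SAP 3.4.1.1), and it gates the PD and CAL testing sequence (SAP 9.1.8).

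**Working it through.** **Inputs.** SAP 9.1.8 sets the level: "The primary analysis, of PD at 6 months will be tested using a one-sided alpha level of 2.5" per cent. Protocol 12.2 gives the planning values: "With alpha of 2.5%, power of 80%, SD of 0.5, and effect difference of 0.25 mm". From these it derives 64 evaluable patients per arm and then inflates for attrition: "By considering 25% of drop out and product switching, 86 patients per arm, i.e., 172 patients in total, are needed". The SDs by visit are assumptions, taken from the 0.40 to 0.50 mm range of Table 7.

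**The plan's own figure.** n per arm = 2(1.960 + 0.842)² × 0.5² / 0.25² = 62.8, so 63 by the normal approximation. The t-based calculation gives 64 (power 80.1%). Then 64 / 0.75 = 85.3, so 86 per arm and 172 in total. The sample size reproduces and is not affected by this point.

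**Formulas.** Take complete data, a separate mean for each group at each visit, and n = 64 per group, so √(2/64) = 0.1768:

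- True SE at V4 = SD₄ × 0.1768.
- Toeplitz model SE at V4 = √((SD₃² + SD₄²)/2) × 0.1768.
- Ratio = model SE / true SE. This depends on neither n nor the correlation between visits.
- Actual one-sided size = 1 − Φ(1.960 × ratio).
- Power at 0.25 mm under Toeplitz = 1 − Φ((1.960 × model SE − 0.25)/true SE); with separate variances, replace the model SE by the true SE.

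**Worked case.** For SD₃ = 0.40 and SD₄ = 0.50, the pooled SD is √((0.16 + 0.25)/2) = 0.4528. The model SE is 0.0800 and the true SE is 0.0884, a ratio of 0.906. The size is 1 − Φ(1.775) = 3.8%.

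| SD V3 | SD V4 | Model SE | True SE | Ratio | Actual size | Power, Toeplitz | Power, separate variances |
|---|---|---|---|---|---|---|---|
| 0.50 | 0.50 | 0.0884 | 0.0884 | 1.000 | 2.5% | 80.7% | 80.7% |
| 0.475 | 0.50 | 0.0862 | 0.0884 | 0.975 | 2.8% | 82.0% | 80.7% |
| 0.45 | 0.50 | 0.0841 | 0.0884 | 0.951 | 3.1% | 83.2% | 80.7% |
| 0.40 | 0.50 | 0.0800 | 0.0884 | 0.906 | 3.8% | 85.4% | 80.7% |
| 0.50 | 0.45 | 0.0841 | 0.0795 | 1.057 | 1.9% | 85.8% | 88.2% |
| 0.50 | 0.40 | 0.0800 | 0.0707 | 1.132 | 1.3% | 90.6% | 94.2% |

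Where Toeplitz shows the higher power, the gain comes from the inflated size.

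**Check with dropout.** A REML simulation used 2,000 trials per scenario, 75 per arm at V3, 64 per arm at V4 and an assumed correlation of 0.6. It was simplified: two groups, no site effect or covariates, and a fixed critical value of 1.979 in place of Kenward-Roger. With SDs of 0.40 and 0.50, the size was 3.8% under Toeplitz by patient, 2.6% under unstructured, and 3.75% with one record per block as the sample code is written. With both SDs at 0.50, the sizes were 2.7%, 2.65% and 2.4%.

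**What does not repair it.** Kenward-Roger allows for estimating the covariance parameters, not for a wrong structure. A random site intercept adds the same amount to both visits, so it cannot represent a difference. The two-parameter fit will normally converge, so the exception for non-convergence is unlikely to apply.

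**The case against.** The strongest reply is that no harm is documented. No section gives an SD by visit, and Table 7 is a planning grid from the literature, not a contrast between V3 and V4. Putting one end of its range at each visit is an assumption. A small gap matters little: a 5% difference in SD moves the size from 2.5% to 2.8%. This stands, and it makes the consequence conditional.

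A reader might go further and infer that the primary test is anti-conservative. The documents do not support that. The SRP timing gives no direction. If anything, a V3 soon after treatment suggests more spread at V3, which is the conservative case. Time since last SRP is also a candidate covariate in SAP 9.5.1.1 and could absorb part of the mechanism, although backward elimination may drop it.

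A reader might also blame the small number of visits. Homogeneous Toeplitz imposes equal variance at any number of visits. Having only two makes it coincide with compound symmetry and makes the general alternative cheap.

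The gingival crevicular fluid (GCF) model in SAP 9.5.3 carries the same sentence, "However, other covariance structures may be used in case of non-convergence", so extending the point to it is tempting. It does not apply there: GCF is sampled only at V2 and V3 (Protocol 7.5.3), which leaves one post-baseline record and no second variance to pool.

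Finally, the plan does evaluate modelling assumptions and residuals (Protocol 12.6, SAP 9.5.1.1). That is a partial safeguard, since no change of structure is attached to what the diagnostics show.

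**Conclusion.** The structural point holds. The plan fixes one variance for V3 and V4, and if the true variances differ, the V4 standard error, confidence interval and p-value are off. The size is an assumption: over SDs of 0.40 to 0.50 mm, the one-sided size runs from about 1.3% to about 3.8%, and it is exactly nominal when the SDs are equal. The power comparison also assumes 64 per group, whereas the product-use categories may be smaller or unequal.

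With complete data and a separate mean for each group at each visit, the point estimate does not change. Missing records or covariates in the model could shift it; that was not sized.

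This is a free improvement to the primary test. It does not show that the planned test will be wrong.

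**What to change.** In SAP 9.5.1.1, replace Toeplitz with an unstructured covariance within patient for V3 and V4, and keep Kenward-Roger and the random site effect. Code it with visit as the repeated effect and the patient as subject, for example `REPEATED visit / subject=subject type=un`.

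Both parts of that line are needed. Making the patient the subject corrects `subject=visit (subject)`, which as written leaves one record per block and drops the within-patient correlation. Naming visit as the repeated effect keeps a patient who has only V4 from having that record read as the first visit, which matters once the variances may differ.

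Apply the same change to CAL, which uses the primary model, and to BoExp, which refers to its sample code. The FAS and Per Protocol analyses inherit it.

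If a fallback for non-convergence is wanted, name the Toeplitz structure by patient. Heterogeneous compound symmetry would not serve, because with two visits it is the same three-parameter model as unstructured.

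The cost is one SAP sentence, one line of code and one extra covariance parameter (three instead of two). Unstructured still assumes one matrix shared by IQOS, cigarette and dual users, as Toeplitz does.

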4. Perform a likelihood ratio test and drop the covariate with the largest p-value for the likelihood ratio statistic if it is more than 0.05.
5. Repeat steps 2 and 3 until no more covariates can be dropped.
6. Refit the final model with the covariates remaining in the model and estimate PD for each product use group using the restricted likelihood method.

Note that other covariates may be added if deemed necessary.

Number of subjects included in analysis, regression coefficients, 95% CI for regression coefficient, p-value for regression coefficient, Least Squares (LS) means (Cigarette User, IQOS User and Dual-User categories), Difference in LS Means (Cigarette User vs IQOS User/Dual-User) and 95% CI for Difference in LS Means will be presented.

The model fit will be assessed by the analysis of the residual (diagnostics) and by comparing the values predicted vs. the observed values (calibration).

Confidentiality Statement

Data and information contained in this document are considered to constitute trade secrets and confidential commercial information, and the legal protections provided to such trade secrets and confidential information are hereby claimed under the provisions of applicable law. No part of this document may be publicly disclosed without the written consent of Philip Morris Products S.A

Primary Analysis of Change from Baseline in PD at V4	
	The residuals, predicted vs observed values from the final model will be plotted.
Target visit	: V4 (6 Months)
Sample code	
ODS GRAPHICS ON;
 
PROC MIXED DATA = X METHOD=ML (REML for final model);
 
CLASS Product_use Subject Visit site;
 
MODEL PD reduction (Dependent variable) = avisit avisit*trt01a 3 4 5 6 7 8 9 10 11 12/ ddfm=kr outp=dsn residuals vciry;
 
RANDOM Site;
 
REPEATED / subject=visit (subject) type=toep;
 
LSMEANS Product_use * Visit / CL ALPHA=0.025 DIFF E UPPER;
 
RUN;
 
Where 1 2 3 4 5 6 7 8 9 10 11 12 refers to the covariates.
 
ODS GRAPHICS OFF;

Output	
15.4.5.1 Primary Analysis of Change from Baseline in Pocket Depth (mm) at V4 with Initial Pocket Depth \geq 4 mm - As Exposed Set -
 
15.4.5.2 Regression Coefficients and Graphical Diagnostics of Primary Analysis of Change from Baseline in Pocket Depth (mm) at V4 - As Exposed Set -
 
15.4.5.3 Primary Analysis of Change from Baseline in Pocket Depth (mm) at V4: Variables Dropped - As Exposed Set -

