	
covariate with the largest p-value for the likelihood ratio statistic if it is more than 0.05.
 
3. Drop one covariate (only covariates 7-12) and re-fit the model.
 
4. Perform a likelihood ratio test and drop the covariate with the largest p-value for the likelihood ratio statistic if it is more than 0.05.
 
5. Repeat steps 2 and 3 until no more covariates can be dropped.
 
6. Refit the final model with the covariates remaining in the model and estimate PD for each product use group using the restricted likelihood method.
 
Note that other covariates may be added if deemed necessary.
 
Number of subjects included in analysis, regression coefficients, 95% CI for regression coefficient, p-value for regression coefficient, Least Squares (LS) means (Cigarette, IQOS and Dual-Users), Difference in LS Means (Cigarette vs IQOS/Dual-user) and 95% CI for Difference in LS Means will be presented.
 
 • Predicted value and observed value will be plotted.
Target visit	: 
 • V3 (3 months) • V4 (6 months)
Sample code	Refer to “ Primary Analysis ”
Output	
15.4.9.1 Exploratory Analysis of Change in Multiplex Assay - As Exposed Set -
 
15.4.9.2 Regression Coefficients and Graphical Diagnostics of Exploratory Analysis of Change in Multiplex Assay - As Exposed Set -
 
-
 
15.4.9.3 Exploratory Analysis of Change in Parallel Reaction Monitoring - As Exposed Set -
 
15.4.9.4 Regression Coefficients and Graphical Diagnostics of Exploratory Analysis of Change in Parallel Reaction Monitoring - As Exposed Set -

Summary Table of (i) MAP (ii)PRM

Population	:	
 • As Exposed Set
------------	---	--

Confidentiality Statement

Data and information contained in this document are considered to constitute trade secrets and confidential commercial information, and the legal protections provided to such trade secrets and confidential information are hereby claimed under the provisions of applicable law. No part of this document may be publicly disclosed without the written consent of Philip Morris Products S.A

Summary Table of (i) MAP (ii)PRM	
	➤ Product use pattern categories
Contents	: In addition to the contents defined in “ Descriptive statistics ”, robust measures for the center (median) and the dispersion (median absolute deviation, MAD), geometric means and CV will be presented as well.

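### SAP 9.5.1.1 does not define one primary model: its two lists of removable covariates disagree on whether cigarette use since randomisation must stay in

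*SAP*

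**What the plan says.** The primary analysis is a repeated-measures mixed model in the As Exposed Set, with three product-use groups: "Estimates of difference in PD will be calculated for Cigarette User against IQOS User categories and Cigarette User against Dual User categories". SAP 9.5.1.1 numbers its covariates as follows:

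- 1-2: the two randomisation strata
- 3-6: V1 full-mouth PD, visit, product use, and visit by product use
- 7: "Average daily cigarette use at each visit"
- 8-9: the interactions of each stratum with product use
- 10: time since last SRP
- 11-12: two tooth-extraction counts
- 13: baseline tooth mobility

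The selection rule is introduced by "Covariates 8-12 will be assessed for adequacy in the model using a step-wise (backward) approach through the following algorithm". Step 3 of that algorithm then says "Drop one covariate (only covariates 7-14) and re-fit the model". Steps 2 and 4 set a likelihood-ratio threshold of p above 0.05 and name no range. The algorithm is followed by "Note that other covariates may be added if deemed necessary". The key to the sample code gives the covariates as "1 2 3 4 5 6 7 8 9 10 11 12", and the numbers in the MODEL line itself begin at 3.

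SAP 5.2.5 builds covariate 7 from cigarettes reported between randomisation and each visit. SAP 5.2 to 5.2.3 classify patients from the same post-randomisation self-reports.

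Protocol 12.6 has a fixed list: the two strata, V1 full-mouth PD, exposure group and its interaction with visit, and site as a random effect. It has none of covariates 7-13 and no selection. SAP section 7 records two changes, both to analysis sets, and does not mention the model.

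**The concern.** A primary test should be reproducible from the plan alone. Here two analysts can each follow a sentence of the SAP and fit different final models, and the disputed term is not a minor one. Covariate 7 is close to a continuous version of the exposure being tested. With it in the model, the contrast compares IQOS and cigarette users at equal cigarette consumption. That is not the hypothesis in SAP 3.4.1, and it removes any benefit that comes from smoking less. With it out, the contrast is the one in Protocol 12.6.

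Elimination and additions can only be done once post-randomisation PD is available. Under SAP 4.3.2 statistician blinding ends at the later of SAP finalisation and database lock, so blinding does not protect this step. The same model is reused for PD at V3 and for CAL (SAP 9.5.2.1) and for the FAS and PP analyses (SAP 9.5.1.2 and 9.5.2.2).

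**Working it through.** **1. The texts side by side.**

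| Covariate | Introductory sentence (8-12) | Step 3 (7-14) | Code key |
|---|---|---|---|
| 7 | must stay | may go | listed |
| 8-12 | may go | may go | listed |
| 13 | must stay | may go | absent |
| 14 | not mentioned | may go, but does not exist | absent |

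The first range allows 2^5 = 32 final models. The second allows 2^7 = 128, because only 7-13 exist. Both counts are before any added covariates.

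No other section settles it. In SAP 9.5.3 both sentences agree ("Covariates 7-12 will be assessed for adequacy in the model using a step-wise (backward) approach through the following algorithm" and "Drop one covariate (only covariates 7-12) and re-fit the model"), and cigarette use is item 8 there, so it is removable. The biomarker model in SAP 9.5.2.1 includes the same term with no removal step.

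**2. The plan's sample size** (Protocol 12.2: one-sided 2.5%, 80% power, SD 0.5 mm, difference 0.25 mm). The normal approximation gives 2 × (1.960 + 0.842)² × 0.5² / 0.25² = 62.8. The t-test version gives 63.77, so 64. Then 64/0.75 = 85.3, so 86 per arm and 172 in total. This reproduces. At 64 per group, SE = 0.5 × √(2/64) = 0.0884 mm and power = Φ(0.25/0.0884 − 1.96) = 81%.

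**3. Covariate 7 kept: closed form, two groups, direct effect.** The documents give no use distribution. Assume cigarette users at mean m and SD s per day, and IQOS users uniform on 0-1 per day (mean 0.5, variance 1/12). Then b = ((m − 0.5)/2)², w = (s² + 1/12)/2, R² = b/(b + w), SE = 0.0884/√(1 − R²), and power = Φ(0.25/SE − 1.96).

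| m / s | b | w | R² | SE (mm) | Power |
|---|---|---|---|---|---|
| 12 / 8 | 33.1 | 32.0 | 0.51 | 0.126 | 51% |
| 17 / 5 | 68.1 | 12.5 | 0.84 | 0.224 | 20% |
| 20 / 3 | 95.1 | 4.5 | 0.95 | 0.414 | 9% |

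**4. Simulation of the selection rule: single visit, two groups of 64, 4,000 runs.** Cigarette users are normal, mean 15 and SD 5, floored at 1. IQOS users are the absolute value of a normal with mean 0.3 and SD 0.3. Strata are even coin flips. V1 PD, SRP time and mobility are standard normal, and extraction counts are Poisson with mean 0.2. None of these affects the outcome. Residual SD is 0.5. Elimination is at likelihood-ratio p > 0.05. In the mediated case the effect is 0.25/14.7 mm per cigarette per day.

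| | Protocol-type model | 7 kept (8-12) | 7 removable (7-13) |
|---|---|---|---|
| No effect: one-sided rejection | 3.1% | 2.4% | 4.0% |
| Direct 0.25 mm: power | 78% | 23% | 79% |
| Through fewer cigarettes: mean estimate | 0.25 mm | 0.00 mm | 0.11 mm |
| Through fewer cigarettes: power | 78% | 3% | 55% |

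The Monte Carlo SE near 2.5% is √(0.025 × 0.975/4000) = 0.25 points. The 3.1% for a model with nominal size shows the noise, so this run alone is weak evidence on error.

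**5. Wider settings.** These use m/s of 17/3, 17/5, 17/8, 12/4, 12/8, 20/3 and 20/8, with 17 dual users at 8 per day (SD 4), three groups and 6,000 null runs each.

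- Protocol-type model: error 2.2%-2.7%, power 78%-80%.
- 7 kept: error 2.4%-2.7%, SE 0.133-0.360 mm, power 11%-47% for a direct effect; mediated contrast −0.02 to 0.00 mm.
- 7 removable: error 3.2%-4.6%, power 77%-78% for a direct effect and 21%-69% for a mediated one.

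A two-visit check (correlation 0.6, Wald tests) at 17/3, 17/5 and 12/8 gave 18%, 25% and 52% power with 7 kept. With 7 removable it gave 78%-79% power and 3.2%-4.6% error. Step 4 states its inputs in full and is the simulation a reader can repeat.

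**The case against.** **The range 7-14 is a stale index.** This is plausible. In the primary list cigarette use sits just before the block 8-12, which can be read as deliberate retention, and the sentence introducing the algorithm arguably sets the scope for every step. On that reading the conflict between lists disappears. But no sentence says so, and the exploratory and biomarker models point in opposite directions. Even then covariate 7 would stay in the primary contrast, selection on outcome data over 8-12 would remain, and so would the open-ended additions.

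**The code is only a sample, and dropped variables are tabulated.** Both are true. The numbers are placeholders, and output 15.4.5.3 discloses the choice. Disclosure does not fix the choice in advance.

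**Section 7 is a minor gap.** Accepted. Protocol 12.1 defers detail to the SAP and requires changes to be documented in the CSR.

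**Ending selection altogether is a preference.** In part. Correcting the index, aligning the code and deleting the additions sentence would cure the textual clash. That would give one algorithm but still up to 32 models, and covariates 10-12 can follow poor response: Protocol 7.6.2 allows extra SRP for worsening and Protocol 6.7 records extractions for worsening.

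**Stronger readings the documents do not support.** A reader might infer that the stated 80% power is simply lost. That depends on use distributions the documents do not give, and the figure defining the groups was not available for this check. A reader might infer that power is safe if covariate 7 is removable. That holds only for a direct effect. A reader might infer that the error rate is held at 2.5% by the 8-12 list or by a fixed model. The groups are formed by actual use (SAP 8.1), so no model here guarantees it. An assumed pre-existing difference of 0.10 mm gives Φ(0.10/0.0884 − 1.96), or about 20% one-sided error, even in the fixed model.

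**Conclusion.** The concern holds as a defect of specification. SAP 9.5.1.1 gives two incompatible removable sets, one of which names a covariate that does not exist. Its code matches neither set, and it permits unspecified additions. Whichever list was meant, keeping covariate 7 changes the estimand of the primary contrast.

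Confidence in the text is high; the sizes are illustrative. They assume 64 per group, SD 0.5 mm, the stated cigarette-use distributions, no site effect and no confounding between self-selected groups. On that basis, against about 80% for a protocol-type model at 0.25 mm:

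- **Covariate 7 kept:** power is roughly 10%-50% for a direct effect, and the contrast is about 0 mm if the effect acts wholly through fewer cigarettes.
- **Covariate 7 removable:** power is about 77%-79% for a direct effect and about 20%-70% for one through fewer cigarettes, with one-sided error of about 3%-4.6%.

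The inflation of error is modest. The larger consequences are for power and for what is estimated.

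**What to change.** Before unblinding, amend SAP 9.5.1.1 as follows:

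- Lock the primary model as the Protocol 12.6 terms (two randomisation strata, V1 full-mouth PD, product-use group, group by visit) plus visit, with site as random effect and no other covariates.
- Delete the backward elimination, its dropped-variable outputs, and the sentence allowing additions.
- State a fixed order of fallback covariance structures for non-convergence; the SAP now allows others without naming them.
- Report the post-randomisation covariates 7 and 10-12, the stratum-by-product interactions 8-9, and baseline tooth mobility (13) only in labelled sensitivity analyses.
- Make the sample code match, including items 1 and 2.
- Use the same structure for PD at V3 and for CAL (with V1 full-mouth CAL). In FAS and PP use it with randomised arm, as SAP 8.2 and 8.3 already require.
- Record the change in SAP section 7.

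The cost is wording and code; N stays at 172. The downside is that imbalance between exposure groups in SRP timing, extractions or baseline mobility, which may be systematic because the groups are self-selected, would be examined only in sensitivity analyses. The locked model does not remove confounding between those groups.
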